**I. Specific Aims:**

- a) To perform a comparative trial of the “Total Capture” hysteroscopy drape (TCD) versus the standard drape during patient surgeries to document improved, real-time determination of patient fluid absorption. Inaccurate detection of fluid absorption by a patient during hysteroscopy is a source of complications, morbidity and mortality from excessive patient fluid absorption. Pilot testing of a prototype design of the “Total Capture” drape versus the conventional hysteroscopy drape indicated remarkable improvement in fluid capture and accurate fluid deficit determination in a plastic pelvic model experiment. The interest from corporate producers of hysteroscopy fluid management systems and drape manufacturers is contingent upon demonstrating “proof of concept” with actual patient surgeries.
  
- b) To evaluate the clinical usefulness of the TCD compared to the Standard drape for hysteroscopy with the standardized metrics of: 1) the Human Factors Surgical Drape Assessment and 2) The System Usability Scale. These metrics will allow us to quantitate clinical usefulness and usability of both the operating surgeons and operating room staff.

## II. Significance

Distention of the uterine cavity is necessary for visualizing the inside of the uterus during hysteroscopy. Continuous turnover of the medium is important to maintain adequate imaging by clearing debris and blood that accumulate during the surgical procedures. Systemic absorption of distention media is directly related to the surgical disruption of veins in the deep endometrium (lining of the cavity) and myometrium (uterine smooth muscle) during surgery. The absorption of media by the patient is directly proportional to the invasiveness of operative hysteroscopy and the distention medium pressure within the uterine cavity.

Patient hazards and complications from imprecise measure of fluid absorption: The safe conduct of hysteroscopic surgery requires precise monitoring of patient fluid absorption of the distending medium used to visualize the intrauterine cavity. The detection of the amount of fluid absorption depends upon the proper collection of the distention medium not absorbed by the patient. Serious patient complications, including hyponatremia (low serum sodium), heart failure, and pulmonary and cerebral edema, can result from over absorption of distending medium (1). Absorption of non-electrolytic distention medium (glycine, sorbitol) can cause an osmotic imbalance between extracellular fluid and brain cells causing life-threatening cerebral edema. Isotonic saline or Ringer's lactate, if absorbed in sufficient volume, have also been associated with fluid overload leading to right-sided heart failure and pulmonary edema (2, 3). These complications could lead to the requirement for intensive care unit monitoring, permanent disability, or even death of the patient.

The incidence of blood electrolyte disturbances following operative hysteroscopy that require monitoring has been estimated to be as high as 5%. The incidence of severe clinical complications of fluid overload associated with operative hysteroscopy has been estimated to be about 0.1% to 0.2% (4, 5). Unfortunately, as described, these complications for women undergoing hysteroscopy can produce serious morbidity or death. In fact, female sex steroids may inhibit enzymes that regulate blood electrolytes, which may explain why premenopausal women are 25 times more likely to die or have permanent brain damage from hyponatremic encephalopathy than men or postmenopausal women (6).

Loss of uncollected distention medium onto the floor and into operating room blankets creates other hazards to the patient and surgical team besides the significant patient risks of fluid absorption. Fluid standing on the operating room floor can pose a fall risk to surgical team members (7). The effluent fluid from the patient that is not collected contains blood and bodily fluids that expose the surgical team to the hazards of infectious disease and biological toxins. Significantly, fluid becomes an electrical hazard when it comes into contact with electrical equipment. Distention medium that escapes capture may come in contact with electrical outlets, switches, and surgical electrodes increasing the risk of burns, fires and damage to equipment.

Additionally, the inaccurate detection of the fluid deficit may pose a clinical dilemma for the hysteroscopic surgeon. Does the surgeon stop a procedure when the fluid management alarm indicates that a fluid deficit (approximate patient fluid absorption) exceeds the safe limit even though they see fluid on the floor? If the surgery proceeds, how long can it safely continue? Without accurate, real-time fluid absorption data, surgeries may be prematurely terminated because of erroneously reported high fluid deficits thus requiring a potentially unnecessary repeat surgery with a delay in cure, increased cost, and more patient risks. The surgical team and healthcare system would certainly be exposed to medico-legal risk if a fluid management alarm sounds, the procedure is continued and the patient suffers a complication of fluid overload.

### **III. Guideline Recommendations for Fluid management During Hysteroscopy**

Use of an automated fluid pump and monitoring system is advocated by both the American College of Obstetricians and Gynecologists and the American Association of Gynecologic Laparoscopists (8, 9). Guidelines for the threshold for acceptable fluid absorption by patients during hysteroscopy have been established by these groups. Most guidelines indicate that a threshold for safe absorption by patients is 500 to 750 mL for non-electrolytic media and 1000 mL for electrolytic medium such as normal saline. Data indicate that fluid absorption of greater than 1000 mL of electrolytic medium is associated with an increased risk of gas embolism (10). It has been shown with routine postoperative CT imaging of the brain that cerebral edema can occur with as little as 500 mL of non-electrolytic distension solutions (1). For other patients with cardiovascular disease or other comorbidities, the threshold for

safe absorption of medium should be reduced. An alarm can be set to sound a warning when a preset volume deficit is reached. Most operating rooms mandate a halt to the procedure following a warning alarm and, in some cases, special post-operative patient monitoring is required for patients to insure fluid and electrolyte normality, adequate pulmonary function, and hemodynamic stability.

#### IV. A Design to Improve the Accuracy of Fluid Deficit Measurements During Hysteroscopy

The problem with current hysteroscopy drapes for fluid management: The actual measurement of the distension medium absorbed by patients is often inaccurate because fluid that is not absorbed into the patient's body is not adequately captured into the collection bag of the surgical drape for return to the fluid management system and deficit calculation. The method for real-time monitoring of patient fluid absorption involves subtracting the volume collected from the volume infused considering all sources from the hysteroscope outflow (11). The sources of outflow include: 1) the perineal collection bag which captures fluid spilled from the cervix but around the hysteroscopy sheath, and 2) the media not captured by the collection bag that spills on the floor or is absorbed into operating room blankets (see Figure 1). Problems are compounded if the person monitoring fluid balance has other duties in the operating room which increases the risk of errors. While conceptually simple, there are a number of difficulties encountered when attempting to collect media from all sources in the operating room environment.

##### Standard Hysteroscopy Drape

[figure not shown]
[figure not shown]

Figure 1.

A proposed solution to the problem: The "Total Capture" Drape (TCD) for hysteroscopy prevents the escape of fluid that would otherwise not be measured by the standard drape because the TCD design includes a continuous sheet of non-permeable plastic that extends above the collection bag (see Figure 2 below).

### "Total Capture" Hysteroscopy Drape

**Figure 2.**

Because of specially designed hand pouches under the sheet, the surgeon can situate the sheet beneath the patient's buttocks without violating sterile technique. The plastic extension sheet, which is continuous with the collection bag, has a "bowl" shaped design to funnel unabsorbed fluid into the collection bag while restricting its lateral flow to prevent fluid loss onto the floor and into blankets. The conventional hysteroscopy drape relies upon an adhesive strip to cause adherence of the drape to the patient's perineum. The conventional design fails because the moisture from unabsorbed fluid destroys the adhesive bond which creates a gap with loss of fluid between and around the buttocks as shown in Figure 1 above. We hypothesize the "Total Capture" Drape design provides an accurate recorded hysteroscopic fluid deficit in real-time so that patient safety and surgical parameters are optimized. The simple design of the TCD would add a very significant

improvement for patient safety and care with minimal cost for the estimated 200,000 hysteroscopies performed per year in the U.S.

## **Experimental Trial with the TCD versus the Standard Hysteroscopy Drape in a Pelvic Model Simulation**

We sought to document whether or not a prototype design of the "Total Capture" drape (TCD) would perform under replicated clinical conditions in a superior fashion compared to the currently marketed hysteroscopy drape. The experimental testing was performed with design assistance and prototype production of the TCD by Medical Murray Engineering and with technical help from Carolinas HealthCare System for access to an operating room suite, the hysteroscopy fluid management system, conventional Cardinal Health hysteroscopy drape, and the ZOE Gynecologic pelvic model. The pelvic model was configured so that all fluid introduced into the artificial vagina would not be absorbed by the model but would flow out of the artificial vagina. The fluid management system can accurately subtract the volume of fluid collected from the volume of inflow fluid introduced to calculate the fluid deficit which would indicate failure of fluid collection. The flow of fluid out the artificial vagina onto the perineum of the ZOE model could then be compared between drapes to determine the relative capture efficiency of fluid lost in this trial. (A video showing the experimental set-up and demonstration of the trial is available.)

### **Data from Trial of Fluid Capture Efficiency of the TCD versus Conventional (Cardinal) Hysteroscopy Drape**

#### **General Observations**

A total of four trials per drape were conducted. The fluid loss (deficit) was calculated by subtracting the collected volume from the inflow volume by the fluid management system. This value should be 0 for all trials since the pelvic model was configured to have no absorption by the model and 100% of the fluid introduced would flow out of the artificial vagina. One trial from each product had procedural difficulties making results invalid. The first trial with the conventional hysteroscopy drape (Cardinal) was invalid because the pressure setting was too high (70 mm hg) instead of the standard 50

[figure not shown]

mm hg; the third trial of TCD was invalid because the saline bag became depleted in the middle of the trial.

**Conventional Hysteroscopy Drape Performance (Cardinal)**

Cardinal			
Duration: 60 sec. Pressure: 50 mmhg	Saline introduced (ml)	Loss (Deficit) (ml)	Comment
Trial No.			
1	1250	340	NA
2	862	482	NA
3	1260	820	NA

Conventional Hysteroscopy Drape Performance

**Observations:**

- The proper functioning of the conventional drape (Cardinal) was dependent on the adhesion of double sided tape, around the inside lip of the fenestration to the perineum.
- The perineal region beneath the vaginal orifice found on the ZOE pelvic model was a best case scenario for the Cardinal product because the model has tacky elastomeric skin, and the model perineum was flat with no curves, clefts, or hair.

[figure not shown]

- Once the adhesive bond was broken, fluid ran down the perineum, behind the drape, not to be returned to the system – accounted for by the system as deficit. During the trials the adhesion did indeed fail and render the drape progressively less effective with each addition trial.

**"Total Capture" Drape Performance**

Total Capture			
Duration: 60 sec.	Saline introduced (ml)	Loss (Deficit) (ml)	Comment
Pressure: 50 mmhg			
1	1255	0	NA
2	1059	0	NA
3	1131	0	NA

**"Total Capture" Drape Performance**

**Observations:**

- The Total Capture Drape did not rely on a skin-to-drape seal in order to function. With an extension flap underneath the patient, fluids running down the perineum were directed into the collection pouch and returned to the system.

- In four trials of the total capture drape, there was no deficit observed.

We concluded that no major design iterations would be required to move the TCD prototype to the next phase of development

**V. Comparative Trial for “Proof of Concept” Testing to Evaluate the Efficiency of the Total Capture Drape Compared to the Conventional Hysteroscopy Drape during Hysteroscopic Surgery**

All women undertaking hysteroscopy are required to have a sterile surgical drape with a fluid capture pouch system to collect the distention media not absorbed by the patient to calculate fluid deficits. Both the TCD and the standard hysteroscopy drape possess the characteristics described above, although design features of the standard drape are deficient. The TCD has received 510(k) FDA determination to be “substantially equivalent” to the standard hysteroscopy drape.

- a. **Subject Recruitment:** All women age 18 and older who are scheduled for an operative hysteroscopy at a CHS operating room facility are candidates for the trial. The research coordinator will be contacted by the physician of upcoming hysteroscopies. At that time, the coordinator will reach out to the patient to see if they are interested in participating. A consent will be emailed to the patient. Written consent will be obtained from patient in preop holding area.
- b. **Risks to the patient:** It will explain that the TCD may not perform in the same manner as the standard drape. It will be shared that the TCD will have met sterilization standards and that there is no evidence that the TCD would substantially alter the surgical risks of the hysteroscopy.
- c. **Exclusions:** Patients will be excluded if they are not acceptable candidates for a hysteroscopy procedure for any reason. Patients will be told that if they do not wish to participate in the trial that they will get the standard care that they normally would have received from their operating surgeon.
- d. **Benefits:** Patients will be told that the drape for surgical use may or may not improve surgical outcome. The information gained from the trial may provide benefit to others undergoing hysteroscopy in the future.

- e. Compensation: Participation in the study will not involve additional costs to the patient, nor will the patient receive any compensation for participation in the study. If complications of hysteroscopy occur during participation in the study, their physician will provide and arrange treatment as necessary, and medical expenses will be billed to the patient's insurance company in the usual manner. Patients will understand that they do not waive any legal rights by signing the study consent.
- f. Withdrawal: It will be explained that the patient's participation in the study is completely voluntary, and that they should not feel under pressure to enter into the study. Withdrawal from the study will not harm their relation with their doctors or the Carolinas HealthCare System.
- g. Confidentiality: The consent will specify that there is a small risk of loss of confidentiality, but the study data from the trial will be de-identified for collection and analysis. Any personal health information will be kept confidential and secure. No publication will reveal the identities of any patients.
- h. Patient Information: In the consent form the patient will be provided the contact information for the principal investigator and that Institutional Review Board approval was required before the conduction of the study.

### Clinical Study Design

---

The primary outcome variable for the comparative trial will be the hysteroscopy fluid deficit (HFD) which can be precisely measured by the fluid management system by subtracting the outflow volume (OV) returned to the fluid management system from the inflow volume (IV). That is:

$$HFD = IV - OV$$

Secondary outcomes include uncollected fluid volume (UFV), occurrence of the alarm sounding for exceeding the fluid deficit limit, and procedure interruption. The UFV is defined as the difference of HFD between TCD and standard drape group. The UFV will be two components as determined by the circulating OR nurse in charge of the fluid management system. The first are the volume on the floor and the volume absorbed by the operation blankets and drapes. The second component is an estimate of any fluid loss from leaking hysteroscopy joints and gaskets not captured by the collection bag. In addition, the time required for procedures will be recorded.

Adverse events and serious adverse events will be captured along with relatedness and severity. We will classify event terms using Common Terminology Classification of Adverse Events version 4.03 (National Cancer Institute).

#### **Measures for Drape Usability, Quality, and Convenience**

We plan to objectively and subjectively evaluate the usability and usefulness of the TCD compared to the standard drape. Staff will be asked to complete the System Usability Scale (SUS) [section XVII SUS; Brooke, 1986] to evaluate their perceived clinical usefulness of the TCD and the standard drape. The SUS is a validated 10-item survey for assessing perceived usability that uses a 5-point Likert scale ranging from strongly disagree to strongly agree. To further subjectively and objectively assess the TCD a human factors and design researcher will observe the surgeries. The human factors researcher will attend the first surgeries to ensure consistent rating with design researcher who will subsequently observe the remaining surgeries until data saturation is reached. The human factors expert will attend any surgeries the design researcher cannot attend. Staff will be asked to speak aloud using the system, which the researcher will record. Further, the researcher will complete an objective human factors assessment tool (section XVII). Finally, enrolled surgeons will be provided the opportunity to participate in one-on-one feedback sessions or focus group sessions to provide suggestions on how they perceive usability of the drape can be improved. These sessions will be facilitated by the Principal Investigator and the design researcher or human factors expert. These metrics will allow us to quantitate clinical usefulness and usability of both the operating surgeons and operating room staff. These results will not only provide this assessment of the TCD compared to the standard hysteroscopy drape (which is used across ORs within CHS) but will also provide important information to improve the drape if deficiencies are identified.

Adverse events and serious adverse events will be captured along with relatedness and severity. We will classify event terms using Common Terminology Classification of Adverse Events version 4.03 (National Cancer Institute).

## **VI. Randomization and Blinding**

We will use standard randomization to allocate patients in a 1:1 allocation to the TCD or the standard hysteroscopy drape. The randomization lists will be generated by a study statistician within [name] team using SAS Enterprise Guide version 6.1. The assignments will be opaque envelopes which ensure allocation

concealment. Once a patient consents and is deemed eligible for the study, the study coordinator will provide the next envelope to the operation nurse who will open the envelope in privacy to learn the allocation. All study staff collecting and recording data for the trial will be masked to the drape that was used during the procedure.

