## VIII. Statistical Methods and Sample Size Justification

The primary outcome for the study is the hysteroscopy fluid deficit (HFD) as determined by the fluid management system by subtracting the outflow volume (OV) from the inflow volume (IV) ( $HFD = IV - OV$ ). Our null hypothesis is  $H_0: \mu_{Standard} = \mu_{TCD}$  where  $\mu$ =mean fluid deficit. Our alternative hypothesis is  $H_a: \mu_{Standard} > \mu_{TCD}$  due to the underestimation of the outflow volume created by the loss of outflow fluid to floors and blankets. If we assume the true absorption rates by the patients are the same between the groups due to randomization, by estimating and testing the difference HFD between the two groups we are estimating and testing a more accurate measure of the uncollected fluid volume (UFV) as shown below:

$$\begin{aligned} \mu_{Standard} - \mu_{TCD} &= (\mu_{Standard, \text{true absorption}} + \mu_{Standard, \text{UFV}}) - \mu_{TCD, \text{true absorption}} \\ &= (\mu_{\text{true absorption}} + \mu_{Standard, \text{UFV}}) - \mu_{\text{true absorption}} \\ &= \mu_{Standard, \text{UFV}} \end{aligned}$$

The primary analysis for the study will use a general linear model on the HFD with a fixed effect for study group (TCD versus Standard drape) controlling for surgeon and indication for hysteroscopy, the stratification factors for the randomization.

Secondary outcomes include estimated uncollected fluid volume from floor and blankets, occurrence of the fluid deficit alarm sounding, stopping of the operation due to concerns of overabsorption by the patient, and adverse events. Estimated uncollected fluid volume will be analyzed similar to the primary outcome. All other outcomes are categorical and will be compared using Chi-square analyses.

We will sample 10 procedures (or until data saturation) from each arm (TCD vs standard) to conduct qualitative assessments on Usability using the Human Factors

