Assessment Tool for the surgeons and operating team members. Once data saturation is reached using the Human Factors Assessment Tool, enrolled surgeons will be provided a step-by-step video link orientation to the Total Capture Drape. For the SUS, we will collect data on attending physicians only on their first and fifth procedures (the study team may change it to 1st and 3rd if deemed appropriate). We will estimate means or medians with standard deviations (or interquartile ranges) for the items and total scores for the SUS. Both within (1st vs. 5th) and between arms (TCD vs. standard) comparison on total scores of SUS will be conducted. We will compare the two groups using linear mixed models or generalized linear mixed models (depending on the distribution) with a random effect for the procedure to control for correlation of the measures among team members participating in the same procedure.

At this early stage of investigation, we have no prior data on HFD in patients to estimate the variability need for the sample size estimation. We have preliminary data from the simulated experiment showing a 100% recovering of loss deficit by the TCD. If we conservatively assume the loss deficit will decrease from 40% to 20% of the inflow volume, this would result in a clinically meaningful improvement with an approximate effect size of 0.92 based on the variability of loss deficit in the simulation. Given this, we are using effect size (relative to standard deviation) as the primary justification for the number of patients needed for the study. With a sample size of n=34 per arm, we would have 81% power to detect an effect size of 0.7 (0.7\*standard deviation of the HFD) with a two sided, two sample t-test ( $\alpha=0.05$ ). To account for potential missing data of 10%, we propose randomizing 76 women (n=38 per arm). With n=34 women in each group, we would also have 80% power to detect an absolute 33% reduction in the proportion of procedures with the alarm sounding due to fluid deficit threshold being reached assuming the proportion in the standard drape arm is 50%. This power was calculated using a Fisher's Exact test for testing proportions between two independent samples. The same power would apply for detecting differences in the proportion of procedures terminated.

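### Does the primary model's reference to stratification factors conflict with a randomization section that names no strata?

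*Combined protocol and SAP*

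**What the plan says.** Section VI (Randomization and Blinding) is the only place that describes how allocation is done. It says "We will use standard randomization to allocate patients in a 1:1 allocation to the TCD or the standard hysteroscopy drape". It adds that "The randomization lists will be generated by a study statistician", and that after consent and an eligibility check "the study coordinator will provide the next envelope to the operation nurse". It gives no stratum, factor level, block size or separate envelope series.

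Section VIII (Statistical Methods and Sample Size Justification) specifies a general linear model for the hysteroscopy fluid deficit (HFD) with a fixed effect for drape, "controlling for surgeon and indication for hysteroscopy, the stratification factors for the randomization". The sample size in the same section rests on a two-sided, two-sample t-test: "With a sample size of n=34 per arm, we would have 81% power to detect an effect size of 0.7". Allowing for 10% missing data gives 38 per arm and 76 in total. The other secondary outcomes, being categorical, are compared by Chi-square without covariates.

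**The concern.** Section VIII treats stratification by surgeon and indication as settled, and the section that should define it does not mention it. Someone who built a list from Section VI alone would have no instruction to stratify, and the coordinator would have no instruction to check surgeon or indication before choosing an envelope.

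Three things could be at stake.

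- The trial report must describe one allocation method, and the two sections do not obviously give the same one.
- Section II says that "The absorption of media by the patient is directly proportional to the invasiveness of operative hysteroscopy", so indication plausibly predicts HFD. Chance imbalance on it would cost precision.
- The Chi-square comparisons of alarms and stopped operations are not adjusted, so an imbalance there would not be corrected.

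**Working it through.** **1. The two sections side by side.** Section VI specifies the ratio, who makes the lists, and how allocation is concealed. Section VIII specifies the factors. Nothing in Section VI rules out strata: it speaks of lists in the plural, and the next envelope can mean the next one in the relevant series. It does not confirm strata either. The sections are incomplete relative to each other but do not contradict each other.

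**2. The plan's own figures.** Inputs from Section VIII: 34 per arm, effect 0.7 SD, two-sided α = 0.05. The noncentrality is 0.7 × √(34/2) = 0.7 × √17 = 2.886 on 66 degrees of freedom, which gives power of 81.2%, against the stated 81%. For missing data, 34/0.9 = 37.8, so 38 per arm and 76 in total. Neither figure uses strata, so neither depends on how Section VI is read.

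**3. Validity.** In simulations with 6 or 10 surgeons and 3 indications, the type I error of the adjusted model was 4.3% to 5.5% whether or not allocation was stratified. Adjusting for a baseline factor does not require having stratified on it.

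**4. Precision if the list is unstratified.** The following are assumptions, because the documents do not give them: numbers of surgeons and indications, R², equal caseloads, 68 of 76 women analysed, and blocks of 2 and 4 within strata.

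Let RSS be the residual sum of squares of the 0/1 arm indicator after regression on surgeon and indication. It equals 17 under perfect balance. Then

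noncentrality = 0.7/√(1 − R²) × √RSS, with df = 68 − rank − 1.

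Example with 7 surgeons and 3 indications, where rank = 9 and df = 58, at R² = 0.3:

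- Single 38:38 list, mean RSS 15.0: 0.837 × √15.0 = 3.24, power about 89%.
- Stratified on both factors, mean RSS 16.3: 0.837 × √16.3 = 3.38, power about 91%.

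Averaged over simulated allocations, at R² = 0.3:

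| Surgeons × indications | Women per cell | RSS, list / both factors | Power %, list / both factors | Loss (points) |
|---|---|---|---|---|
| 3 × 2 | 12.7 | 16.2 / 16.8 | 91.2 / 92.2 | 1.0 |
| 5 × 3 | 5.1 | 15.5 / 16.6 | 89.8 / 91.8 | 2.0 |
| 7 × 3 | 3.6 | 15.0 / 16.3 | 88.8 / 91.3 | 2.5 |
| 10 × 4 | 1.9 | 13.9 / 15.4 | 86.4 / 89.7 | 3.3 |
| 15 × 4 | 1.3 | 12.6 / 14.2 | 82.6 / 87.1 | 4.5 |

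As information, 3 × 2 loses 68 × (1 − 16.2/16.8) = 2.4 women and 15 × 4 loses 68 × (1 − 12.6/14.2) = 7.7 women.

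**5. The unfavourable end, R² = 0.** Power on a single list in the same five settings is 79.1, 77.1, 75.8, 72.7 and 68.1%. The more precise stratified scheme adds 1.5, 2.8, 3.6, 4.9 and 7.5 points, giving 80.6, 79.9, 79.4, 77.6 and 75.6%. That scheme uses both factors in the first three settings and surgeon only in the last two. Stratification recovers part of the shortfall from 81%, but every setting stays below 81% with it. The remainder comes from fitting these covariates when they explain nothing, and the plan fits them on either reading.

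**The case for a change.** The strongest case for a change is that a core design feature should not have to be inferred, and that settling it costs one sentence. If the lists were in fact unstratified, calling the factors stratification factors in the report would be wrong.

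Chance imbalance is also not remote. On a single 38:38 list, a surgeon or indication group of 10 has a 31% chance of splitting 7:3 or worse. If Section VI means simple randomization, there is a 30% chance that the smaller arm has 33 or fewer of the 76.

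Part of this stands. Section VI would read better with the factors named, and the precision cost is real and grows with the number of surgeons. It does not amount to a defect in the plan, for these reasons.

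- The report will describe the lists as they were generated. If they were unstratified, surgeon and indication are simply pre-specified covariates and no result changes.
- Chance imbalance in an unadjusted secondary comparison is part of what its error rate already covers.
- Section VIII plans 38 per arm, which fits a balanced list better than simple randomization. Even a 33:43 split keeps (33 × 43/76)/(38 × 38/76) = 18.67/19 = 98% of the information.
- The largest losses need 10 to 15 surgeons. The plan takes usability ratings as follows: "we will collect data on attending physicians only on their first and fifth procedures". If every surgeon reached five cases there could be about 76/5 = 15, but the plan does not require that and allows first and third instead. The figure of 15 is therefore only illustrative.
- Prescribing a scheme has its own cost. Small blocks within surgeon make the next allocation easier to guess for surgeons, who see the drape and, under Section V.a, notify the coordinator of upcoming cases. With fewer than about 2 women per cell, stratifying on both factors was less precise than stratifying on surgeon alone. The documents do not give the counts needed to weigh these costs.

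**Conclusion.** The mismatch in wording is real, but it is a gap in operational detail that the study statistician can fill from Section VIII of the same document. On either reading the hypothesis, primary model, sample size and stated power are the same, and the primary comparison is valid.

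The only consequence of an unstratified list is some precision. The loss is about 1 to 2.5 power points with 3 to 7 surgeons at R² = 0.3, about 1.5 to 3.6 at R² = 0, and about 4.5 with 15 surgeons and 4 indications at R² = 0.3 against stratifying on both factors. These sizes rest on assumed surgeon and indication counts, assumed R² and equal caseloads. Whether adjusted power lies above or below 81% depends mainly on how much variance the two factors explain, which the documents do not show. No change to the plan follows.
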